# D. Description, Risks and Justification of Procedures and Data Collection Tools:

Potential Risks: Studies have examined the risk of using fluorescein for multiple purposes with no serious side effects [21]. The FDA has already approved the use of sodium fluorescein in adults and children for diagnostic angiography of the retina and it is also widely used as a contrast agent. The dose and route of administration being used in this study are consistent with the FDA approval for use of this drug in children.

The use of intravenous sodium fluorescein in gastrointestinal procedures has been reported to be extremely safe. Side effects from these studies include nausea/vomiting, injection site erythema, rash, and epigastric pain. Other investigators have examined the safety profile of intravenous fluorescein use in angiography. In these studies, reported potential side effects of sodium fluorescein administration include, urticaria, syncope, respiratory reactions, cardiac reactions, and hypersensitivity reactions. Multiple mechanisms have been suggested such as vasovagal phenomenon, histamine release via a nonallergic pathway, and sympathetic discharge related to anxiety as the pathogenetic basis of these side effects. The most common symptoms (>20%) reported in these studies include malaise, headache, dizziness, and nausea/vomiting [22-24].

A reported side effect of Fluorescein is yellowish skin for 6-12 hours after administration and yellow urine for 24-36 hours after administration. Fluorescein is systemically cleared by 48 to 72 hours after administration.

The package insert for Fluorescein describes "care must be taken to avoid extravasation during injection as the high pH of fluorescein solution can result in severe local tissue damage." To alleviate this risk, the medication will be given IV push over 10 seconds.

Confidentiality of Study Data: Data including enrollment, study drug orders, pre-operative and postoperative exams and adverse event reporting will remain identifiable. De- identification of this information is not possible as patient identifying information is necessary for continued

[name]: 18-0242 Page 7 Version: 07/03/2019

patient safety monitoring and follow-up while in the trial.

Data that is collected clinically and analyzed for this study will remain identifiable in the patient's medical record but will be de-identified in the research records. Identifying information will be replaced with a unique study-specific code. All documents will be handled in accordance with the HIPPA policy and the Children's Hospital Colorado "Research Data – Ownership, Use, and Retention" policy. Only members of the research team will have access to the study documents and they will be stored on a password protected, encrypted computer on the secure Children's Hospital Colorado server. Paper documents will be stored in a locked filing cabinet in the secure administration pavilion at Children's Hospital Colorado.

Privacy Protections: Every effort will be made to protect patient privacy. Patients enrolling in the study will be informed with whom their information will be shared and they will sign a combined consent/HIPAA authorization form. Patients will not be identified if the study results are published or presented at a scientific meeting.

#### E. Potential Scientific Problems:

One possible limitation of this study is the single-institution nature of the project. Because Children's Hospital Colorado is a high-volume center, we are confident that we will be able to enroll the number of subjects needed for successful data analysis. Once this pilot project is complete, one of the future directions will be to conduct a multi-site study that can account for inter-institutional variance.

Another possible limitation is the absence of randomization to a control arm. We plan to use resection rates reported in the literature, as well as historical controls from our institution to compare to tumor resection rates during this pilot study.

# F. Data Analysis Plan:

Annually at the Children's Hospital of Colorado, roughly 80 patients present with tumors requiring neurosurgical interventions. Prior adult population studies had enrolled between 10 – 40 patients. Importantly, these studies have largely involved single tumor types. Our study involves multiple tumor types and locations and would warrant increased enrollment for statistical analysis. Additionally, extent of surgical resection is an important outcome in our project. Using data extrapolated from adult studies, such as the most recent Niera et al. study, 32 patients were enrolled and compared to historical controls for tumor resection. This study demonstrated differences in extent of resection. Given the population and nature of our study, about 1/10 of the patients whom qualify for this study will be spine patients and the rest will be cranial with varying types of tumor pathology. [19]

Furthermore, if we use the number from this study [Niera] patients with fluorescein use had an average resection rate of 93.1% versus 77.1% for non-fluorescein historical control patients [19] Power calculations using a one-way ANOVA with alpha=0.05 power at 70%, 80%, and 90%, a mean difference of 16% (93.1-77.1) and a standard deviation of 25% are shown in Table 3.

Table 3: Power Calculation			
Power	N Total		
70%	64		
80%	80		
90%	106		

[name]: 18-0242 Page 8 Version: 07/03/2019

Our pediatric neurosurgery/ neuro-oncology program benefits from a robust tumor program with multiple historical patients with reliable clinical follow-up that assesses for post-operative neurologic reactions. However, we do not believe that randomization is feasible in our study. The overall prevalence of pediatric brain tumors and the nature of the pathology would not allow our center the ability to perform a randomized trial in a meaningful time-frame. Our trial is designed to be a multi-year trial and randomization would double the study time for enrollment and greatly decrease feasibility to perform this study.

Given this, we propose a 3:1 ratio of historical controls to fluorescein treated patients to match tumor location and histology. 150 historical controls will be pulled from the last ten years of Children's Hospital patients and matched to the 50 fluorescein treated cases on lesion location and pathology. This 3:1 ratio will strengthen our ability to objectively assess for adverse events related to sodium fluorescein as well as our extent of tumor resection analysis. Importantly, historical controls undergo stereotactic-guided tumor resection in a similar fashion to patients undergoing fluorescein administrations as outlined in our protocol.

All patients who undergo sodium fluorescein-aided resection will also have neuropathological analysis. We will analyze correlation of fluorescein staining to histopathology. Tissue obtained during the time of surgery will be used to correlate fluorescein staining to histopathological diagnosis. This data will be used to calculate sensitivity and specificity of fluorescein staining for tumors. Pre- and post-operative imaging will be used to assess the degree of the extent of resection in intraparenchymal tumors. Data collected from post-operative follow-up will be used to assess for potential complications/adverse reactions associated with sodium fluorescein administration.

For data analysis, extent of tumor resection will be compared as a continuous value across groups using a parametric ANOVA. Further calculations, such as sensitivity, specificity and positive predictive value will be calculated by contingency tables. Additionally, since group membership is not random we will run an adjusted analysis predicting the likelihood of tumor resection as a continuous outcome adjusting for demographic and co-morbidity factors. Significance will be assigned at p < 0.05.

Furthermore, adverse reactions and population/demographic data will be characterized using relative risk and odds ratios. Overall survival and progression free survival analysis will be characterized using Kaplan-Meier curves and compared across groups using a log rank test.

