#### IV. Research Methods

### A. Outcome Measure(s):

The primary outcome measure will be extent of tumor resection. For all patients, pre-operative imaging and post-operative imaging will be used to analyze the extent of resection of the tumors. In intracranial lesions, the use of volumetric imaging tools will be used to calculate the extent of tumor resection. In spinal lesions, manual measurement will be used to determine the extent of resection.

Secondary outcome measures include the subjective utility of fluorescein per the operating surgeon, as well as positive predictive value, sensitivity and specificity for extent of tumor resection. Additional outcome measure(s) will vary depending on the neurosurgical tumor removed. Intraoperative videos and images will be collected from the surgical case. Images obtained will be correlated to tissue biopsy and will aid in the analysis of fluorescein

[name]: 18-0242 Page 2 Version: 07/03/2019

extravasation in pediatric neurosurgical tumors. All tissue samples collected will be taken for histopathological analysis.

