#### **Exclusion Criteria:**

- Tumor in functionally eloquent cortex that precludes maximal surgical resection
- Severe renal dysfunction
- Preoperative serum creatinine level > than normal range and GFR < 30.

- Severe liver dysfunction
- History of asthma or pulmonary spasm
- Known allergy to sodium fluorescein or any other contrast dye
- Previous administration of sodium fluorescein within the last 72 hours
- Pregnant or nursing mother
- Other unspecified reasons that, in the opinion of the investigator, make the subject unsuitable for enrollment.
- Tumors with primary differential diagnosis not included in the inclusion groups

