# C. Study Design and Research Methods

## Study Design:

This study will be a prospective non-randomized cohort study with patients presenting to Children's Hospital Colorado for resection of a central nervous system tumor. Due to heterogeneity of the pediatric central nervous system tumors and the evidence available, we will have a planned initial cohort (first phase) that will include tumor pathology that will allow us to test the feasibility of the study and the preliminary activity of fluorescein in the pediatric population. After completion of this initial cohort, we will expand our study to include tumors that are more specific to the pediatric population.

Currently, there exist many tumor types where there is robust literature on the use of fluorescein [3,4,6-15,21-26,27-29]. We plan to enroll patients based on a phased system and after completion of the first phase, we will perform a safety analysis as outlined below.

[name]: 18-0242 Page 3 Version: 07/03/2019

After safety analysis is completed, we will either proceed to the next phase, or in the event there is a safety concern, the DSMC will terminate our study. Terms for termination are detailed below.

Enrollment of ten patients is planned for each tumor type in each of the phases. The phases are designed to assess patients where evidence is available and proceed to tumor types where pediatric evidence is limited and the tumors are more unique to the pediatric population. This will allow us to safely assess patients and allow us to expand our trial in a controlled fashion. After completion of each phase of enrollment, we will continue enrolling the prior phase patients for a maximal total of 10 patients per each pathology group. Thus, maximal enrollment will be 20 patients for the first phase pathologies and 30 patients for the second phase pathologies, for a total enrollment of 50 treated patients and 150 historical controls

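### Historical controls are matched on lesion location and pathology only, are not clearly subject to the eloquent-cortex exclusion, and are compared without adjustment for tumour size, so the extent-of-resection comparison is open to selection bias of unknown size

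*Combined protocol and SAP*

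**What the plan says.** Extent of resection is the primary outcome (section IV.A). It is measured from pre- and post-operative imaging, with volumetric tools for intracranial tumours. "In spinal lesions, manual measurement will be used to determine the extent of resection".

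The exclusion list in section IV.B includes "Tumor in functionally eloquent cortex that precludes maximal surgical resection". It belongs to the description of the population to be enrolled, whose inclusion criteria require consent.

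Section IV.F draws the controls from the hospital's last ten years at 3:1, "matched to the 50 fluorescein treated cases on lesion location and pathology". No other matching factor and no eligibility rule for controls is given. Section IV.C plans "for a total enrollment of 50 treated patients and 150 historical controls", which is the only wording that might carry the enrolment criteria over to controls.

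On analysis, section IV.F says that "extent of tumor resection will be compared as a continuous value across groups using a parametric ANOVA". Because group membership is not random, it adds a model "adjusting for demographic and co-morbidity factors". It does not list those factors or say which of the two analyses carries the conclusion.

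Section IV.E acknowledges the lack of randomisation: "We plan to use resection rates reported in the literature, as well as historical controls from our institution" are to be compared with the study's results. Section IV.F also says that "historical controls undergo stereotactic-guided tumor resection in a similar fashion". Section IV.C has post-operative images read by neuroradiologists who are unaware of fluorescein use.

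**The concern.** The eloquent-cortex exclusion is a pre-operative judgement that the tumour cannot be maximally resected. It therefore selects on expected extent of resection, which is the primary outcome. Applied to treated patients alone, it would raise that group's mean with no help from the dye. For this criterion the direction is known: any imbalance left after matching favours fluorescein.

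Location matching may remove part of the imbalance, but the plan does not say how finely location is matched. Two tumours coded to the same location can still differ in resectability. Pre-operative tumour size is a second baseline feature that neither the matching nor the named covariates cover, and the direction of any imbalance in it is unknown.

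At stake is the meaning of a significant result at p < 0.05. As written, the plan could not cleanly separate a fluorescein effect from a difference in who was selected.

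**Working it through.** **1. The plan's own figure.** Table 3 uses a 16-point difference, SD 25 and alpha 0.05. A two-group one-way ANOVA is equivalent to a two-sided t test. With equal groups, the noncentral t gives totals of 64, 80 and 106 for 70%, 80% and 90% power. Table 3 reproduces exactly.

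**2. Precision at the planned sizes.** For 50 treated and 150 controls:

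- SE = 25 × √(1/50 + 1/150) = 4.08 points.
- Smallest significant difference = 1.972 × 4.08 = 8.05 points (t, 198 df).
- Power for 16 points = 97%.

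Sample size is therefore not the weak point. More controls would reduce random error but not bias.

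**3. How many controls the criterion could affect.** Section IV.C plans 10 treated patients per tumour type. At 3:1 with matching on pathology, that is 30 controls per type. The criterion concerns cortex, so two cases are shown:

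- High-grade glioma only: 30/150 = 0.2 of controls.
- Both first-phase gliomas (high-grade glioma and pilocytic astrocytoma): 60/150 = 0.4.

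**4. Size of the shift.** Bias = share affected × fraction of those ineligible × their deficit in extent of resection. The documents give neither of the last two. Both are assumptions: 20% (range 10-30%) and 30 points (range 20-40). No reduction for location matching is taken yet.

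| Affected controls | Central bias | False-positive rate | Range of bias | Range of rate |
|---|---|---|---|---|
| High-grade glioma only | 0.2 × 0.20 × 30 = 1.2 | about 6% | 0.2 × 0.10 × 20 = 0.4 to 0.2 × 0.30 × 40 = 2.4 | about 5% to 7-9% |
| Both first-phase gliomas | 0.4 × 0.20 × 30 = 2.4 | about 8-9% | 0.4 × 0.10 × 20 = 0.8 to 0.4 × 0.30 × 40 = 4.8 | about 5% to 17-22% |

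The rates assume no true effect and a nominal 5% test. Where two values are given, the higher is the noncentral t with SD 25 in both groups. The lower is a simulation of 40,000 runs in which the ineligible controls also widen the control SD.

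**5. Effect of location matching.** If it halved the imbalance, the central figures would fall to 0.6 points (5.2%) and 1.2 points (about 6%). Finer matching would reduce them further.

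**The case against.** The strongest reply is that matching is to treated cases already screened for eloquence. If location is matched finely, few controls in eloquent cortex could qualify, and almost all of the imbalance might go. The plan also counts controls within total enrolment, concedes non-randomisation, adds literature rates and an adjusted model, describes similar surgery for controls, and uses blinded image readers. It calls itself a pilot.

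Part of this stands. The bias may be small, and location matching could make it negligible. But the plan neither defines location nor states control eligibility. Similar technique and blinded reading address co-intervention and measurement, not selection. Literature rates are also a non-randomised comparator. Pilot or not, the plan sets a significance test on this comparison.

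A reader might infer more than the documents support, in three ways:

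- **All cranial controls are affected.** The exclusion is limited to cortex, and nothing in the documents extends it to medulloblastoma or ependymoma. Even for pilocytic astrocytoma the larger case may be generous, since one cited study concerns tumours of the vermis.
- **Leaving year of surgery out of the adjusted model is a fault.** Controls may largely precede treated cases, so year would be close to a proxy for group. If all controls precede treated cases and treated accrual takes 2-5 years (assumptions), adding year cuts power for 16 points to about 68-77%. The documents give no evidence of a time trend.
- **Repeat or emergent surgery biases the result.** Re-enrolment is permitted, but no frequency or imbalance is given. Whether a past emergency left time for consent may not be recoverable from charts. Neither is a ground for this point.

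**Conclusion.** The concern holds as a risk of bias, not as proof of it. The omissions are plain in the text: two matching factors, no clear eligibility rule for controls, no tumour size or matching factors in the named analyses, and no statement of which analysis decides. If the eloquent-cortex criterion is not applied to controls, any imbalance that remains favours fluorescein.

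The magnitude rests wholly on assumed inputs. At the central ones it is modest, 1.2 to 2.4 points against a critical difference of 8.05. A reader might infer that a positive result would be uninterpretable, but these figures do not show that. The point should be fixed because the bias falls on the primary outcome, its direction is predictable, and the remedy is cheap.

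**What to change.** 1. State that controls must meet the enrolment criteria that can be judged retrospectively: age, tumour type and the eloquent-cortex criterion. Judge them from pre-operative records and scans, before the post-operative result is seen. This only approximates the surgeon's prospective judgement, but it puts both groups under the same rule.
2. Prespecify that the extent-of-resection conclusion rests on the adjusted model. Include pathology, location and pre-operative tumour size (volume for intracranial lesions, manual measurement for spinal lesions, handled within stratum). Name the demographic and co-morbidity covariates in advance and keep them few, since there are only 50 treated patients, 10 of them spinal.
3. Address era only by a sensitivity analysis limited to the most recent controls. Do not put year of surgery in the concluding model.

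The cost is protocol wording plus extra chart and scan review; pre-operative imaging is already used for the primary outcome. Screening may leave fewer controls. At 2:1 (50 v 100) the SE rises from 4.08 to 25 × √(1/50 + 1/100) = 4.33, and power for 16 points falls from 97% to 96%. A sensitivity analysis on the last five years (75 controls if spread evenly, an assumption) has SE 25 × √(1/50 + 1/75) = 4.56 and power of about 94%. Make these choices before control outcomes are examined.

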## b. Definition of Adverse Events (AE)

Adverse event means any untoward medical occurrence associated with the use of a drug in humans, whether or not considered drug related (21 CFR 312.32 (a))

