# ii. Relationship to Study Intervention:

A study team member, who is a Licensed Independent Provider (LIP) will be responsible for determining the relationship of each AE to the study intervention.

- Definitely Related There is clear evidence to suggest a causal relationship, and other
  possible contributing factors can be ruled out. The clinical event, including an abnormal
  laboratory test result, occurs in a plausible time relationship to study intervention
  administration and cannot be explained by concurrent disease or other drugs or chemicals.
  The response to withdrawal of the study intervention (dechallenge) should be clinically
  plausible. The event must be pharmacologically or phenomenologically definitive, with use
  of a satisfactory rechallenge procedure if necessary.
- **Probably Related** There is evidence to suggest a causal relationship, and the influence of other factors is unlikely. The clinical event, including an abnormal laboratory test result, occurs within a reasonable time after administration of the study intervention, is unlikely to be attributed to concurrent disease or other drugs or chemicals, and follows a clinically reasonable response on withdrawal (dechallenge). Rechallenge information is not required to fulfill this definition.
- Potentially Related There is some evidence to suggest a causal relationship (e.g., the event occurred within a reasonable time after administration of the trial medication). However, other factors may have contributed to the event (e.g., the participant's clinical condition, other concomitant events). Although an AE may rate only as "possibly related" soon after discovery, it can be flagged as requiring more information and later be upgraded to "probably related" or "definitely related", or downgraded to ..., as appropriate.
- Unlikely to be related A clinical event, including an abnormal laboratory test result, whose temporal relationship to study intervention administration makes a causal relationship improbable (e.g., the event did not occur within a reasonable time after administration of the study intervention) and in which other drugs or chemicals or underlying disease provides plausible explanations (e.g., the participant's clinical condition, other concomitant treatments).

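### For events judged related to the dye, and for dye-specific effects, the planned relative risk and odds ratio cannot be computed and the 150 controls add nothing; they help only for events both groups can have

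*Combined protocol and SAP*

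**What the plan says.** IV.F plans 50 treated children and 150 historical controls: "150 historical controls will be pulled from the last ten years of Children's Hospital patients and matched to the 50 fluorescein treated cases". One stated reason for the ratio is safety: "This 3:1 ratio will strengthen our ability to objectively assess for adverse events related to sodium fluorescein". The measure follows two paragraphs later: "adverse reactions and population/demographic data will be characterized using relative risk and odds ratios". No other summary of safety data is given in IV.F, and the sentence does not name the comparator or the event. IV.F also says: "Data collected from post-operative follow-up will be used to assess for potential complications/adverse reactions associated with sodium fluorescein administration".

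Relatedness is a formal classification in this protocol. Under IV.G.1.d.ii, a licensed practitioner on the study team is responsible for "determining the relationship of each AE to the study intervention", on a five-step scale that turns largely on timing after administration. The adverse event definition in IV.G.1.b is wider: "any untoward medical occurrence associated with the use of a drug in humans, whether or not considered drug related". IV.G.1.e records all events from administration of the dye, to 7 days for non-serious and 30 days for serious events.

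IV.D lists known effects of fluorescein. Some are specific to the dye (yellowish skin, yellow urine). Most are not (vomiting, headache, dizziness, rash).

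**The concern.** The benefit claimed for the controls is tied to events related to fluorescein. A control child had no injection against which relatedness could be judged, so that child's count of related events is zero whatever happened after surgery. The same holds for discolouration caused by the dye. An analyst who takes IV.F at its word would try to form a ratio with a structural zero in the denominator.

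Two things are at stake. First, the stated statistic is not available for the events that bear most directly on the safety of the dye. Second, the plan gives no interval in its place. Section IV.H requires approval by the Data and Safety Monitoring Committee (DSMC) before the second phase. Neither IV.F nor IV.H tells that committee how large a reaction rate remains compatible with the first-phase data.

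A smaller point: the same sentence applies ratios to demographic data. Neither ratio exists for age taken as a continuous variable, and eligibility runs from 31 days to 21 years.

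**Working it through.** **Inputs.** 50 treated and 150 controls (IV.F); up to 20 children in a full first phase (IV.C). The documents give no event rate, precision target or power for safety. Rates marked *assumed* are mine.

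**The plan's own figures.** 3 × 50 = 150 controls, which agrees. Table 3 is reproduced exactly by a two-group comparison with standardised difference 16/25 = 0.64 and two-sided alpha 0.05: totals of 64, 80 and 106 for 70%, 80% and 90% power. Table 3 concerns extent of resection only, so nothing in it sizes the safety comparison.

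**A. Events judged related, or dye-specific.** With x such events in the treated group:

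- RR = (x/50) ÷ (0/150): undefined.
- OR = [x/(50 − x)] ÷ [0/150]: undefined.
- Adding 0.5 to each cell does not rescue it. For x = 3, RR = (3.5/51) ÷ (0.5/151) = 20.7 with 150 controls, and (3.5/51) ÷ (0.5/51) = 7.0 with 50. The answer is set by how many structural zeros are entered.
- Fisher's exact test has the same defect: 3/50 against 0/150 gives p = 0.015, and against 0/50 gives p = 0.24.

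The information lies in the treated children alone. For zero events in n children, the upper limit is 1 − 0.05^(1/n) (one-sided 95%) or 1 − 0.025^(1/n) (two-sided Clopper-Pearson):

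| Events/children | One-sided 95% upper limit | Two-sided 95% upper limit |
|---|---|---|
| 0/20 | 13.9% | 16.8% |
| 0/50 | 5.8% | 7.1% |

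The control count does not enter either formula. With events present, the two-sided limits are 0.05% to 10.6% for 1/50 and 3.3% to 21.8% for 5/50. For an *assumed* true rate of 1%, the chance of seeing at least one event is 1 − 0.99^20 = 18% in 20 children and 1 − 0.99^50 = 40% in 50.

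**B. All-cause events that both groups can have.** Here SE(log RR) = √[(1 − p_t)/(50·p_t) + (1 − p_c)/(m·p_c)], where p_t and p_c are the treated and control risks and m is the number of controls. At an *assumed* 20% in both groups:

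- m = 50: √(0.080 + 0.080) = 0.400.
- m = 150: √(0.080 + 0.0267) = 0.327, a reduction of 18%.
- The 95% half-width of the risk difference falls from 15.7 to 12.8 percentage points.

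Over *assumed* control rates of 5% to 40%, the reduction in SE(log RR) is about 18% at RR = 1 and 26% to 35% at RR = 2. Power for 20% against 40% rises from 59% to 79%. The chance of no control event among 150 is 0.95^150 = 0.05% at a 5% rate and 0.99^150 = 22% at a 1% rate, so an empty denominator is unlikely here unless the event is rare. These figures ignore the matching.

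**The case against.** The strongest reply is that the plan never says the ratios use events adjudicated as related. IV.F does not refer to the relatedness scale. IV.G.1.b and IV.G.1.e cover all events whatever their cause, and IV.F introduces the historical patients by their follow-up for neurologic reactions after surgery. Comparing all-cause rates in exposed and unexposed patients is a standard way to judge whether a drug causes an event. Most reactions listed in IV.D can follow neurosurgery without the dye, and those are the ones that need a comparator. Even an injection-site reaction can follow any intravenous line.

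This stands for all-cause events, as part B of the working shows. A reader might infer from the zero-denominator argument that the controls are useless for safety, that the ratios are undefined throughout, or that the 3:1 safety claim should be struck out. The documents support none of these.

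The reply does not remove the narrower point. The text says related to the dye, no sentence restricts the ratios to all-cause events, and no control window or method of collection is given. IV.G.1.f takes many shared surgical events out of standard reporting. IV.G.1.e still documents every event, but nothing says which ones enter the ratio.

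It is also fair to say that the limits in part A describe any study with 20 or 50 treated patients and no events. They do not measure harm done by a ratio. They show what should be reported in its place.

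**Conclusion.** The point holds for two classes of event: those adjudicated as related to fluorescein, and dye-specific effects such as skin or urine discolouration. For these the planned ratios cannot be computed and the 150 controls carry no information. Zero events would leave rates up to 16.8% (0/20) or 7.1% (0/50) within the two-sided 95% interval. For all-cause events the planned ratios are sound in principle and the extra controls reduce random error.

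A reader might also infer that decisions on continuing the trial would rest on an undefined ratio. They would not: in IV.H the DSMC reviews the events themselves, and no ratio appears in the stopping criteria. The loss is that the committee and the final report have no planned interval for these events.

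The conclusion assumes that the historical controls received no fluorescein, that all 20 first-phase children have been treated when the review takes place (fewer would widen the limit), and that each child is counted once. The all-cause precision figures rest on assumed control rates. The demographic point is minor: ratios can describe categorical characteristics but not continuous age.

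**What to change.** Amend IV.F as follows.

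- Limit the safety benefit claimed for the 3:1 ratio to all-cause events that both groups can have. List those events, including the non-specific symptoms in IV.D and the perioperative complications, and count them over one window that starts from surgery in both groups.
- Give relative risk, odds ratio or risk difference with 95% limits for the listed events only. State how they are collected from control records. More controls reduce random error but not bias from unlike collection.
- Report related and dye-specific events as incidence in treated children with Clopper-Pearson 95% limits, at the first-phase DSMC review and at the end. Count per child, because IV.C allows re-enrolment under the same study number.
- Summarise age and other continuous demographics by standardised differences.

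This changes wording and needs no extra patients. The common window may require some further abstraction from control charts. The downside is a visibly less favourable safety statement: with no related event in 50 children, the report could say only that rates above about 7% are excluded.
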